**Secondary**

Establish if there is any discomfort associated with the ultrasonic propulsion treatment.

Qualify and quantify associated complications from the ultrasonic propulsion procedure.

Demonstrate the ability to move stones in a controlled direction.

Demonstrate the ability to move both large stones ( $> 5$  mm) and small stones ( $\leq 5$  mm).

Demonstrate the ability to move an obstructed stone and an associated reduction in pain and/or hydronephrosis.

Demonstrate a reduction in stone volume

Sponsor: \_\_\_\_\_  
[name]

Date: \_\_\_\_\_

Principal Investigator: \_\_\_\_\_  
[name]

Date: \_\_\_\_\_

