## 1.2 Study Procedure

Patients suspected of having a stone will be screened for this study. Those who meet the study criteria of the population group for which they belong and indicate initial willingness to participate to the clinical staff will be approached by research staff. The research staff will explain the study and obtain informed consent.

After consent, if the subject does not have recent clinical imaging of their stone(s), the subject will receive imaging to determine eligibility. The imaging could include: a low dose CT, an abdominal x-ray, an ultrasound, or a combination of an ultrasound and abdominal x-ray. All subjects must have clinical imaging, obtained as part of their standard-of-care or as a research activity, indicating stones or fragments are present. Otherwise the subject will be removed from the study.

For patients receiving only watchful waiting or medical expulsion therapy (population 1a), the investigative study may occur the same day as the clinic visit, or be rescheduled on a different day. For the pre-surgery SWL and URS participants (population 1b), the investigative study will occur on the same day as (but prior to) the surgical procedure. For the URS surgical participants (population 2), the study will occur during the surgical procedure. For the post SWL and URS participants, the investigative study will occur after 4 weeks post treatment. The subjects will receive imaging confirmation of a stone fragment. For subjects suspected of having an acute obstructing stone, the study may occur during the same visit or be rescheduled on a different day. The study will take place after management of their pain.

Population Group	Treatment Routine Care	Treatment Investigative Study
1a: Observation/medical expulsive therapy	Pass naturally	As available
1b: Scheduled for SWL	SWL	Day of, but before SWL
1b: Scheduled for URS	URS	Day of, but before URS
2: Scheduled for URS	URS	During URS procedure
3: Post SWL; Post URS fragments	Pass naturally	After 4 weeks as available
4: Obstructing stone	Medical management	As available

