Study Treatment – Investigative – All Subjects: The investigational examination is expected to take 30 minutes to 1 hour and will be performed by either a certified sonographer or physician identified as an investigator for this study and previously trained on the device. The study will take place after consultation with at least one urologist and with at least one physician in attendance.

- a) Prior to the ultrasound study, participants will complete a baseline pain questionnaire.
- b) A photo of the subject's skin in the region where the probe will be positioned will be taken.
- c) Participants will undergo a diagnostic ultrasound examination by a certified physician or sonographer with the investigational device. The sonographer and physician will verify the stone is visible on ultrasound and near the location identified on the most recent diagnostic imaging, if available.

- d) Audio and video of the exam will be recorded. Select images of the kidney anatomy and stone will also be captured using the screen capture functionality of the investigational software. A second photograph of the skin in the region where the probe was positioned will be taken between the screening examination and stone pushing.
- e) Participants will undergo stone pushing with the investigational device. The operator will begin with low output and increase the output as necessary. The subject will be directly asked if they experienced any sensations with each of the first three pushes. The subject will be advised to report if they feel any change in sensation with the remainder of the study – they will no longer be asked directly. A maximum of three pushes should be attempted from a single probe position and focus. If the stone does not relocate, the operator should alter the angle of approach by (first) rotating the probe to a new angle of approach, (second) repositioning the probe, and (last) repositioning the subject for a more optimal transducer to stone angle (i.e. so as to not push the stone against the tissue wall.)

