- f) The study staff will monitor the real-time ultrasound image during each burst applied. If echogenicity related to cavitation within the tissue is observed, the treatment will be paused for 1 minute. The treatment will resume at a reduced dose level. This procedure will be repeated as echogenicity related to cavitation in the tissue is continued to be observed. If the treatment setting is reduced to 50 W/cm^2 and cavitation is still observed, the study will be stopped.
- g) Select ultrasound images extending over the duration of the Push and a listing of the system settings, including the target location and Push power, will be recorded automatically to the system hard drive. The output voltage, patient position, stone position, and result of the Push burst will also be recorded manually. There are three potential types of motion for each push pulse, 1) no motion, 2) moved but trapped within a confined space, such as a calyx, 3) translation of the stone to a new location. A fourth option that can be recorded is U) unintended Push. This occurred occasionally with the animal studies through accidental activation of the touch screen.
- h) With Probe 1 (C5-2 transducer) a maximum of 120 Push bursts will be delivered in a single session and a maximum of 40 Pushes will be delivered to a single location. With the SC-X probe, a maximum on-time of 5 minutes will be delivered in a single session. If the operator switches probes, the sum of the percentage of the limits of use for either probe cannot exceed 100% (e.g., 90 pulses with the C5-2 probe is 75% of the total 120, so 25% of the 5 minute total, or 1 minute 15 s total ON time could be used with SC-X.)
- i) Participants will immediately undergo a second diagnostic ultrasound exam to confirm the location of the stone after treatment. Audio and video of the exam will be recorded and select images of the kidney anatomy and stone will also be captured.
- j) A third and final photograph of the skin in the region where the probe was positioned will be taken at the conclusion of the investigational study.
- k) Participants will complete a second questionnaire at the completion of the exam addressing any discomfort or pain they may have felt related to the procedure.

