#### Additions for participants with an obstructing stone

- A urine culture will be ordered for all subjects undergoing treatment to evaluate for the definitive presence of infection in follow-up.

Follow up – Routine Care: As part of the routine treatment patients may be asked to strain their urine and retain stones. Patients may also be prescribed alpha blockers to facilitate stone passage, as well as pain medications to take as needed. Surgical (SWL and URS) participants will also be seen for an ultra-low-dose CT, plainfilm KUB and/or renal ultrasound exam post treatment, as standard care.

Follow up – Investigative –Subjects Undergoing Ultrasonic Propulsion or Enrolled in a Control Group: Research staff will contact the patients each week for three weeks and review their charts each week for the longer of a) 90 days or b) follow-up imaging has been completed to

assess for acute colic events, stone passage, and/or additional interventions/adverse events. Subjects will be asked to record the date of any stone passage since the investigational study. Pain medication taken by the participant will be recorded and converted to Morphine equivalents. With the exception of subjects who underwent the investigational study prior to their surgical treatment, all subjects will be scheduled for follow-up visit if it is not already prescribed as part of their routine care. The subject will be scheduled either for a low dose CT, plainfilm KUB, ultrasound, or a combination of KUB and ultrasound as follow-up. In the case of multiple study treatments, the subject will undergo only 1 follow-up CT; ultrasound and/or plainfilm KUB will be used for any additional follow-up requirements. A certified letter will be sent to any subjects lost to the three week follow-up or post-study imaging visit. The letter will be sent if the subject cannot be reached within four weeks following the study.

In addition, specifically for participants with an acute obstructing stone, subjects will be telephoned with the results of the urine culture test when infection is indicated. This may occur through standard-of-care or by the research team.

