### **1.3 Study Analysis**

Safety will be determined by the frequency and severity of any adverse events. Effectiveness of the device will be measured by the % of stones moved and average distance of stone motion. The frequency of stone motion in the desired direction (i.e. toward the UPJ or away from the UPJ) will also be assessed. For the observation/medical expulsive therapy population (1a) and stone fragment population (3), the time between treatment and any reported stone passage will be an additional effectiveness parameter. For the obstructing stone population (4), change in pain status and hydronephrosis status, in addition to time between treatment and any reported stone passage, will be additional effectiveness parameters. Sub-categories will include the average number of pushes and the average treatment time.

Safety of ultrasonic propulsion: Safety is a difficult parameter to establish, particularly for the obstructing stone population who are already experiencing symptoms and subjects receiving SWL and URS treatment, since both these procedures may result in potential confounding

complications (see Table 2). In addition, all patients, at any time, could experience complications associated with the natural passage of a stone, such as renal colic, irrespective of having received our investigational treatment.

A method for evaluating complications associated with the investigational study is listed in the bullet points below. Adverse events (AEs) that occur during or after the study will also be subdivided into procedure AEs and device AEs. Procedure AEs are defined as morbidity / mortality events that may occur no matter what device is used. Examples include heart rate changes during treatment, anesthesia issues, discomfort from lying on an exam table, or for this case, intermittent urinary obstruction and other pain events associated with kidney stones. Examples of device AEs include irritation where the probe was in contact with the skin or an AE that occurs as a result of a software issue.

- The number and level of procedural and device AEs identified during and after the investigational procedure will be established.
- The number and severity level of the AEs will be compared with potential occurrences with routine care.
- Medication use will be reported for each subject. The results will be compared against the baseline level of pain medication used by the general stone population that falls within the same treatment group.

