- Short-term complications (within 90 days) identified from follow-up contact and medical chart reviews will be recorded including type and frequency. The results will be compared to the types and frequency of complications expected in stone patients on average.
- The presence and degree of hydronephrosis will be compared between the research study visit and follow-on clinical visit. The result will be compared to stone patients on average.

Effectiveness of ultrasonic propulsion: The pre- and post- ultrasound images, video data, and manual data recorded during each push pulse will be used to evaluate stone motion. The motion associated with each push will be categorized based upon the following criteria: 1) no motion, 2) moved but trapped within a confined space, such as a calyx, 3) translation of the stone to a new location, or U) unintended activation of the Push pulse. The distance achieved for motion #3 and an estimate of the total distance moved for the entire treatment will also be determined. Lastly, the anatomical position of each stone will be identified. From these data, quantitative measurements can be made as to the effectiveness of the clinical device in moving stones. The analysis can be made over all subjects, but also broken down based on group, stone location, or stone size groupings.

- % occurrence of each motion level achieved per total number of pushes
- % occurrence of each motion level achieved as a function of anatomical location.
- Average distance moved for motion levels 3
- Total distance moved per stone

- For subjects enrolled in the long term study, % occurrence of clinical stone events and length of time to those events from the investigative study.

Stone Passage: Stone passage will be identified either from the subject urine screen, chart review, or post-treatment imaging compared to pre-treatment imaging. If the stone was captured and sent for stone analysis, the size and type of stone will also be documented.

- The number of ultrasonically treated stones that passed (spontaneously without additional surgical procedures) will be reported.
- If available, the time between the investigational ultrasonic intervention and stone passage will be recorded.

Metrics for Success: The following metrics will be used as a measure of success for an individual study.

- By any measure, the stone moved more than 2 mm.
- The treatment procedure was tolerable to the patient.

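### In the acute-stone group, the pain and hydronephrosis measures as written cannot separate a device effect from natural course and ongoing medication

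*Protocol*

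**What the plan says.** The Study Objectives (Secondary) include: "Demonstrate the ability to move an obstructed stone and an associated reduction in pain and/or hydronephrosis". Section 1.3 carries this into the analysis of population 4: "change in pain status and hydronephrosis status, in addition to time between treatment and any reported stone passage, will be additional effectiveness parameters". Neither place names an instrument, a time point or a size of reduction. Table 1 in section 1.1 gives the acute group 22 treatment cases and 0 controls. Section 1.1 admits patients to it on renal colic or on hydronephrosis or ureteral dilation.

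The measurements are described elsewhere:

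- **Before the session.** Section 1.2 states for acute subjects: "The study will take place after management of their pain". The session may be on the same visit or another day. Step a, for all subjects: "Prior to the ultrasound study, participants will complete a baseline pain questionnaire".
- **End of the session.** Step k is a "second questionnaire at the completion of the exam addressing any discomfort or pain they may have felt related to the procedure". Step i is an ultrasound straight after the pushes. Its stated purpose is to confirm where the stone is, and kidney images are captured.
- **Later.** Under safety in section 1.3: "The presence and degree of hydronephrosis will be compared between the research study visit and follow-on clinical visit". The result is set against average stone patients. Follow-up imaging is "scheduled either for a low dose CT, plainfilm KUB, ultrasound, or a combination of KUB and ultrasound as follow-up". Weekly contacts over three weeks cover colic, passage, interventions and analgesic use in morphine equivalents.
- **Success.** The last item under Metrics for Success in section 1.3 joins lower pain, lower hydronephrosis and absence of emergency intervention by an "or", over three weeks.

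**The concern.** With no concurrent control, only a within-patient change measured close to the pushes could be linked to moving the stone. The measures described are not of that kind. Pain starts from a level already lowered by treatment, and the closing questionnaire appears to ask about something else. Hydronephrosis is compared after an interval in which stones may pass and usual medication continues.

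Two things are at stake. An improvement could be reported as support for the objective when it would have occurred anyway. Conversely, a real immediate effect could be missed because pain was already low or was not asked about in comparable terms. A current-pain score that was never collected cannot be recovered at analysis.

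**Working it through.** The protocol gives no target, power or test for this objective, so there is no figure of its own to reproduce. The check sets the passages side by side and adds two illustrations.

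**1. Pain.** The order in section 1.2 is pain management, then questionnaire (a), then pushes, then questionnaire (k). Analgesia that is already effective at (a) lowers the baseline and leaves less room to fall, which works against the device. Analgesia still taking effect, or given later as usual care, lowers pain afterwards and works for the device. The protocol does not let the two be netted. Questionnaire (k) is described as "addressing any discomfort or pain they may have felt related to the procedure". As worded, that is procedural tolerability and not a repeat of the stone pain scored at (a). The weekly contacts list no pain score.

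**2. Hydronephrosis.** The one comparison described is research visit against a later clinic visit. Between the two, the stone may pass and medication continues. Follow-up imaging may be a KUB film alone, and a plain film does not grade hydronephrosis. The ultrasounds at steps c and i bracket the pushes, but no hydronephrosis grade is specified on them.

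**3. Success metric with an inert device.** Inputs: n = 22 (Table 1); need for intervention under medical therapy q = 7% to 26% (Table 2). Assumption: q applies to acute cases over three weeks and to emergency intervention. The protocol says none of these.

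Expected number meeting the item through absence of intervention alone = n × (1 − q):

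- q = 26%: 22 × 0.74 = 16.3
- q = 7%: 22 × 0.93 = 20.5

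**4. Before-after change with zero device effect.** The protocol plans no such test, so this only shows how an uncontrolled comparison behaves. Let each of 22 cases improve naturally with probability π, worsen with probability w, and otherwise stay unchanged. Unchanged includes anyone without the sign at baseline. With i improving and j worsening, count the outcome as significant if P(Bin(i + j, ½) ≥ i) ≤ 0.025, and sum the multinomial probabilities of all such (i, j).

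| π (assumed) | w (assumed) | Chance of a significant improvement |
|---|---|---|
| 5% | 5% | below 0.1% |
| 20% | 5% | 12% |
| 30% | 5% | 38% |
| 40% | 5% | 65% |
| 50% | 5% | 83% |
| 50% | 10% | 63% |
| 60% | 5% | 94% |

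Every π and w is an assumption; the documents give no natural improvement rate for this group.

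**The case against.** The strongest reply is that this is an unblinded, first-in-human feasibility study. The objective is one of six secondary ones, it asks for an associated reduction rather than a causal estimate, and section 1.3 leaves instrument and timing open. An analysis plan, not shown, may settle them. This stands as far as it goes and limits the severity. It does not remove the point, because what is asked at steps a and k, and what is graded at steps c and i, are data-collection choices that analysis cannot repair.

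A reader might infer several stronger things that the documents do not support:

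- **That any fall would reflect analgesia and natural resolution and not the device.** The text shows only that they cannot be told apart.
- **That the protocol fixes the efficacy measure at the later visit.** That comparison is a safety item covering all groups; the effectiveness parameter has no time point.
- **That the two questionnaires certainly do not pair.** The forms are not shown, and the URS exceptions in section 1.2 describe the closing one as a post-study pain questionnaire. It may hold a current-pain item, but the protocol does not say so.
- **That the immediate ultrasound serves only to locate the stone.** Steps d and i capture images of kidney anatomy, and section 1.3 uses pre- and post-treatment images to assess motion.
- **That studying patients after pain management is an error.** It is consistent with the commitment not to withhold or delay standard care.
- **That all 22 cases could show either improvement.** Entry is on either sign, so some may lack one at baseline.

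A same-session measure also has limits. Nothing in the protocol shows that hydronephrosis changes within the 30 to 60 minutes of a session. Restricting to subjects in pain invites regression to the mean, and splitting 22 cases by stone movement is not a randomised comparison.

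**Conclusion.** The point holds in this limited form. As written, the measures for population 4 cannot separate a device effect from natural course and ongoing medication, and the post-analgesia baseline may also conceal a true effect. The net direction of bias is unknown.

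The size cannot be fixed from the documents. Under the stated assumption about Table 2, roughly 16 to 20 of 22 cases would meet the last success item without any device effect. Under assumed natural improvement of 20% to 60% with 5% worsening, an uncontrolled before-after test would look positive in 12% to 94% of repetitions.

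The defect should be fixed, but it does not threaten the study. It affects one secondary objective; the primary objective, repositioning stones, is untouched.

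**What to change.** For population 4, with no change to pain management:

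1. **Pain.** Ask the same current stone-pain item at steps a and k, separately from the procedure-discomfort question. Record the time and type of the last analgesic. Report change for all subjects and, descriptively, for those with non-zero baseline pain.
2. **Hydronephrosis.** Grade it on the ultrasounds at steps c and i. Among subjects with hydronephrosis at baseline, report same-session change by whether the stone moved, alongside the later-visit change.
3. **Later results.** Label later-visit and three-week results as natural course plus treatment. For hydronephrosis, use only follow-up imaging that can show it. Do not count absence of emergency intervention as evidence for this objective.

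The cost is one repeated question, one analgesic field and a grade read from images already taken, with no added visit or procedure. The price is smaller denominators, and same-session change in hydronephrosis may miss a delayed effect. That is why the later change is kept alongside it. The collection items need to be in place before further acute subjects are treated.

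### The controlled-direction objective is scored against a desired direction that the protocol never has recorded before the push

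*Protocol*

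**What the plan says.** The secondary objectives of the Protocol include: "Demonstrate the ability to move stones in a controlled direction". Section 1.3 Study Analysis turns this into a measure: "The frequency of stone motion in the desired direction (i.e. toward the UPJ or away from the UPJ) will also be assessed". It does not say which direction is desired for which group of patients, stone location or push.

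Section 1.2 Study Procedure, step g, sets out what is kept for each push. Part is automatic: selected ultrasound images across the push, and "a listing of the system settings, including the target location and Push power, will be recorded automatically to the system hard drive". Part is manual: "The output voltage, patient position, stone position, and result of the Push burst will also be recorded manually". The result is coded by type of motion: "There are three potential types of motion for each push pulse, 1) no motion, 2) moved but trapped within a confined space", with translation to a new location as the third type and U for an unintended push.

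Other records exist. Section 1.2 says of the examination: "Audio and video of the exam will be recorded". A second ultrasound examination straight after treatment confirms where the stone lies. A second, blinded reader reviews images to confirm representative documented movement.

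**The concern.** Control means that the stone went where the operator meant it to go. To show it, two things are needed for each push: the direction intended, fixed beforehand, and the direction observed. The protocol provides for the second and not the first.

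Without a prior record of intent, someone has to decide afterwards what was desired. The study is unblinded, so that decision can be made with the motion already known. A translation in either direction could then be credited as desired, and a high frequency would show only that stones moved. The primary objective already covers that, so the secondary objective would add nothing.

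**Working it through.** The protocol states no expected rate, threshold or sample size for this measure, so there is no figure to reproduce. The check sets the measure against the records available to build it.

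**What the measure needs, and where it could come from**

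| Record (Protocol section) | Observed direction | Intended direction before the push |
|---|---|---|
| Manual entries, 1.2 step g | Not coded; stone position and result help | Not listed |
| Result code 1, 2, 3 or U, 1.2 step g and 1.3 | No direction in the code | No |
| Automatic images, 1.2 step g | Yes, by reading them | No |
| Target location and power, 1.2 step g | No | Not stated to give a direction of travel |
| Audio and video, 1.2 steps d and i | Yes, by reading them | Only if the operator happens to say it; no step asks for this |
| Post-treatment ultrasound, 1.2 step i | Yes, for net displacement | No |
| Blinded second reading, end of 1.2 | Confirms movement; direction not mentioned | No |

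The observed column can be filled from stored material. The intended column has no required source.

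The bulleted outputs in 1.3 follow the same pattern. They begin with the percentage "occurrence of each motion level achieved per total number of pushes" and go on to location and distance. None concerns direction, so they do not supply the missing definition.

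**What follows for the measure**

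This illustration rests on an assumption that is not in the documents. Suppose T stones are translated with no operator control, a of them toward the UPJ and T − a away from it. Write q = a/T.

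- Direction fixed beforehand as toward the UPJ: share desired = a/T = q.
- Direction fixed beforehand as away: share desired = (T − a)/T = 1 − q.
- Direction named after the motion is seen, in the extreme case: share desired = (a + (T − a))/T = 100%, whatever q is.
- Full control with the direction fixed beforehand: share desired = T/T = 100%.

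The last two lines give the same result, one with no control and the other with complete control. The documents give no value for q, so the share under a preset direction could lie anywhere from 0 to 100%. The conclusion does not depend on q.

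**The case against.** The strongest reply is that the record is richer than the manual entries alone. Images, system settings with target location, audio, video and an immediate repeat examination are all kept, and 1.3 says that images, video and manual data will be used to evaluate motion. This stands as far as observed direction goes: it would be wrong to infer that it is lost because the result code omits it. It does not supply intent. Target location is listed as a system setting, and nothing says that it gives an intended path.

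Second, the bracket in 1.3 may simply list the two possible aims, with the right one depending on the case. That is a fair reading. A reader might infer that the protocol counts either direction as success for the same push; the text does not say so. But the assignment is unwritten. An analysis plan could assign a direction by population or stone location, yet it could not recover the intent of each push if nobody recorded it.

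Third, a reader might infer from 1.2 step e that the aim changes during a session, since "the operator should alter the angle of approach by (first) rotating the probe to a new angle of approach". That step applies when a stone fails to relocate, and its stated purpose is a better angle that avoids pushing the stone into the tissue wall. It does not show that the intended direction changes.

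Fourth, the study uses case report forms that are not shown, and one may hold this field. If so, step g need only name it.

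Finally, this is one secondary, descriptive measure in an early feasibility study. That is true and limits the weight of the point.

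**Conclusion.** The point holds as a gap in data capture. The protocol scores an objective about control against a desired direction, does not fix that direction in advance, and does not require the operator's intent to be recorded. Labelling after the event is possible under the plan; the documents do not prescribe it or show that it has happened.

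The size cannot be taken from the documents. The extreme case of 100% agreement without any control is a bound under the stated assumption, not an estimate. A reader might be tempted to set a 50% chance rate because there are two directions, and to test against it. Nothing in the protocol supports equal probabilities, and it gives no number of stones for this measure, so neither a chance benchmark nor a margin of error can be justified.

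The primary objective of repositioning stones and the success metric of movement beyond 2 mm do not use direction and are unaffected. The conclusion assumes that no form outside the protocol already captures intent before each push.

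**What to change.** In 1.2 step g, add the intended direction (toward or away from the UPJ), entered before each push or each new probe position. In 1.3, define the measure as observed direction agreeing with recorded intent. Report it descriptively with two denominators: all pushes with recorded intent, and the level 3 motions among them. Set no chance benchmark.

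For the images that the blinded second reader already examines, have the direction read without sight of the recorded intent. This does not require extending that reading to every push.

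The note to Table 1 shows that recruitment has begun. Report cases treated before the change separately, because their intent cannot be back-filled.

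The cost is one extra field, a sentence in 1.3 and a few seconds per push or probe position. The reader has one more item to code on images already under review. The treatment procedure itself does not change.
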